15.6.15.2. SLE Medication Categories

| Medication Category | Rule |
|---------------------|--|
| Anti-malarials | Set to "ANTIMALARIALS" if the preferred term begins with "QUINACRINE", "QUININE", "HYDROXYCHLOROQUINE", "MEPACRINE", or "CHLOROQUINE" AND the route of administration is not 'TOPICAL', 'VAGINAL', 'CONJUNCTIVAL', 'INTRANASAL', 'INHALATION', 'INTRA-OCULAR', 'INTRATRACHEAL', 'EPIDURAL', 'INTRA-ARTICULAR', or 'OTHER'. |
| Steroids | Set to 'STERIODS' if at least one associated ATC code (ATCCD1 – ATCCD6) begins with 'H02' AND Route of administration is "INTRADERMAL", "INTRAMUSCULAR", "BUCCAL", "PARENTERAL" "INTRAVENOUS", "ORAL", "SUBCUTANEOUS", or "INTRA-ARTICULAR". |

| Medication Category | Rule |
|---------------------|--|
| Immunosuppressants | Set to 'IMMUNOSUPPRESSANTS' if at least one associated ATC code (ATCCD1 – ATCCD6) begins with 'L04A' or the preferred term begins with "CYCLOPHOSPHAMIDE" (oral and parenteral routes) or "MERCAPTOPYRINE" (oral route) AND route of administration is not "TOPICAL" or "OPHTHALMIC" AND not classified above as "ANTIMALARIALS". |
| NSAIDs | Set to NSAIDs if at least one associated ATC code (ATCCD1 – ATCCD6) begins with 'M01A'. Glucosamine and Chondroitin not considered NSAIDs |
| Aspirin | Set to "ASPIRIN" if CMDECOD contains "ACETYLSALICYLIC ACID" or "ACETYLSALICYLATE LYSINE". |
| Prohibited | Set to "PROHIBITED" if at least one associated ATC code (ATCCD1 – ATCCD6) begins with 'L04AB' or 'V98' or if any of the following conditions are met, if CMDECOD equals , "BELIMUMAB", "ADALIMUMAB", "ETANERCEPT", "INFLIXIMAB", "CERTOLIZUMAB", "TOCILIZUMAB", "GOLIMUMAB", "RITUXIMAB", "ABATACEPT", "ANAKINRA", "CANAKINUMAB", "USTEKINUMAB", "BRODALUMAB", "SECUKINUMAB", "IXEKIZUMAB", "EPRATUZUMAB", "TABALUMAB", "ATACICEPT", "IMMUNOGLOBULIN" (IV route), "CYCLOPHOSPHAMIDE" (IV route), or "PLASMAPHERESIS" |

15.6.15.3. General Conventions

- Assessment of dose is based on analysis dose. Analysis dose is daily dose adjusted for dosing frequency, and in the case of steroid is converted to prednisone equivalents. Exception is intra-articular dose where analysis dose is not populated.
- In the event there are multiple visit dates within a visit window, the date for determining treatment failure, will be the earliest date at which efficacy data (from SLEDAI-2K (IBA), SLEDAI-2K (PI), PGA, and SLE Flare) is recorded. This may be different than the earliest visit within that window.
- If a critical visit (Week 52, 64 , and 104], is missing from efficacy data (from SLEDAI-2K (IBA and PI), PGA, SLE Flare, LLDAS) then the date is imputed as the target day for that visit.
- Actual visit date, not target visit date, is used to assess treatment failures.
 - If the subject’s Day 169 (Week 24) study visit occurs on Day 171, the date for Day 171 is used when applying the treatment failure rules.
- Prohibited medications/dosages started on the date of early withdrawal are considered a TF (see clarification below for steroids). If the prohibited medication/dose starts after the date of withdrawal it will not be part of the TF assessment.

- All potential TF rule violation are output programmatically and all adjudicated.
- Clinical may amend the date of TF during adjudication if, for instance, a subject did not meet the criterion on the date identified by the program but did meet it later.

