7.1. Primary Efficacy Analyses

7.1.1. Endpoint / Variables

The protocol defined primary endpoint is the proportion of participants with a state of disease control defined as a SLEDAI-2K score ≤ 2 (IBA), achieved without immunosuppressants and with corticosteroids at a prednisone equivalent dose of ≤ 5 mg/day at Week 52 (Protocol Section 4).

The protocol Section 10.4.1 Efficacy analysis then clarifies that:

For participants who withdraw prematurely from study treatment and for who subsequent collection of data is not possible, it will be assumed for the primary analysis that they are treatment failures. A dropout/treatment failure = non-responder (DO/TF=NR) analysis will be used .

Hence when adopting the ICH Estimands and Sensitivity Analysis in Clinical Trials E9 R1 addendum terminology, this endpoint is defined as:

| Disease Control |
|--|
| 
Responder:
 
 • SLEDAI-2K score ≤ 2 (IBA); and • Not a TF at the current or any prior visit (TF includes consideration of corticosteroids and immunosuppressants); and • Did not withdraw from the study prior to the visit 
Non-Responder:
 
 • SLEDAI-2K score > 2 (IBA); or • TF at the current or any prior visit (TF includes consideration of corticosteroids and immunosuppressants); or • Withdrew from the study prior to visit (which includes study withdrawal, lost to follow-up and death) |
| 
The derivation of SLEDAI-2K score is provided in Section 15.6.3, treatment failures are defined in Section 15.6.15. and withdrawal from the study prior to Week 52 in Section 5.9.
 |
| 
Note: Discontinuation of study investigational product (belimumab or rituximab) is NOT a component of this endpoint, subjects who discontinue investigational product will only be non-responders if they also meet one of the criteria above.
 |

Note this clarification of notation does not change the protocol-specified primary analysis.

The analysis of the primary endpoint of Arm A vs Arm B will use data from treatment Arms A, and B only.

An exploratory analysis of the relative performance of Arm B vs. Arm C will also be conducted, using data from Arms B and C only.

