15.3. Appendix 3: Assessment Windows

15.3.1. Definitions of Assessment Windows for Analyses

The data is analyzed as per the planned visit assignment.

Exit/withdrawal and unscheduled visits will be slotted to the appropriate planned visit. The assigned visit is based on the interval in which the Study Day for the exit/withdrawal or unscheduled visit falls according to intervals (inclusive) provided below. For completeness, the table also includes visits which are not slotted; these visits will have 'na' for 'not available' listed for the Interval Start and End Day.

| Analysis Set / Domain | Parameter (if applicable) | Target ¹ | Analysis Window | | Analysis Timepoint Number ⁴ | Analysis Timepoint |
|---------------------------------------|---------------------------|---------------------|---------------------|---------------------------|--|--------------------|
| | | | Beginning Timepoint | Ending Timepoint | | |
| All | All | NA | NA | NA | 10 | Screening |
| Year 1 Treatment Phase visits: | | | | | | |
| All | All | 1 | NA | NA | 20 | Baseline |
| | | 29 | 2 | 35 | 30 | Week 4 |
| | | 43 | 36 | 49 | 40 | Week 6 |
| | | 57 | 50 | 70 | 50 | Week 8 |
| | | 85 | 71 | 98 | 60 | Week 12 |
| | | 113 | 99 | 126 | 70 | Week 16 |
| | | 141 | 127 | 154 | 80 | Week 20 |
| | | 169 | 155 | 175 | 90 | Week 24 |
| | | 183 | 176 | 189 | 100 | Week 26 |
| | | 197 | 190 | 210 | 110 | Week 28 |
| | | 225 | 211 | 238 | 120 | Week 32 |
| | | 253 | 239 | 266 | 130 | Week 36 |
| | | 281 | 267 | 294 | 140 | Week 40 |
| | | 309 | 295 | 322 | 150 | Week 44 |
| | | 337 | 323 | 350 | 160 | Week 48 |
| 365 | 351 | 392 | 170 | Week 52 | | |
| 365 | na | Na | 175 | Survival-W52 ² | | |
| Year 2 Phase Visits: | | | | | | |
| All | All | 421 | 393 | 434 | 180 | Week 60 |
| | | 449 | 435 | 476 | 190 | Week 64 |
| | | 505 | 477 | 532 | 200 | Week 72 |
| | | 561 | 533 | 588 | 210 | Week 80 |
| | | 617 | 589 | 644 | 220 | Week 88 |
| | | 673 | 645 | 700 | 230 | Week 96 |
| | | 729 | 701 | 742 | 240 | Week 104 |

| Analysis Set / Domain | Parameter (if applicable) | Target ¹ | Analysis Window | | Analysis Timepoint Number ⁴ | Analysis Timepoint |
|-----------------------|---------------------------|---------------------|---------------------|------------------|--|----------------------------|
| | | | Beginning Timepoint | Ending Timepoint | | |
| | | 729 | na | na | 245 | Survival-W104 ² |
| | | Na | na | na | 250 | Follow-Up ³ |

NOTES:

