¹ Study Day with Baseline/Treatment Start Date as Day 1. Baseline record will be derived in each analysis dataset, analysis visit number will be 15.

² Survival visit for subjects who withdraw from the double-blind treatment phase but consent to the Week 52 and Week 104 survival assessments.

³ The follow-up visit occurs 8 weeks after last dose of belimumab for subjects who discontinue study treatment and withdraw from the study up to (i) Week 52 in Arms A and B or (ii) Week 104 in Arm C.

⁴ If there are multiple visits within a visit window, the visit closest to the target date will be used. If there are two visits equidistant from the target date, then the scheduled visit will be given preference, if both are unscheduled then the first assessment will be used.

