15.6. Appendix 6: Derived and Transformed Data

15.6.1. General

| |
|--|
| 
Multiple Measurements at One Analysis Time Point
 
 For continuous data, the mean of the measurements will be calculated and used in any derivation of summary statistics but if listed, all data will be presented. For continuous data, if there are two values within a time window (as per Section 15.3.1) the value closest to the target day for that window will be used. If values are the same distance from the target, then the scheduled assessment will be used, if both assessments are also unscheduled then the 1st assessment will be taken. For categorical data, if there are two values within a time window (as per Section 15.3.1) the value closest to the target day for that window will be used. If values are the same distance from the target, then the value prior to the target day will be taken. Participants having both High and Low values for Normal Ranges at any post-baseline visit for safety parameters will be counted in both the High and Low categories of “Any visit post-baseline” row of related summary tables. |
| 
Study Day
 
 Calculated as the number of days from First Dose Date: 
 Ref Date = Missing → Study Day = Missing Ref Date < First Dose Date → Study Day = Ref Date – First Dose Date Ref Date ≥ First Dose Date → Study Day = Ref Date – (First Dose Date) + 1 |

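### The treatment-failure cut-off can fall before the SLEDAI-2K that is scored, so rescue in between may go uncounted: any rescue at Week 52, mainly non-steroid rescue at Weeks 64 and 104

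*SAP*

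**What the plan says.** - **Cut-off for failure.** SAP 15.6.15.3 states that, with several dates in a window, "the date for determining treatment failure, will be the earliest date at which efficacy data" exist. The sources are the blinded assessor's (IBA) SLEDAI-2K, the investigator's (PI) SLEDAI-2K, the PGA and the flare record. The next item imputes a date when Week 52, 64 or 104 is missing, so the convention is meant for the key visits.
- **Value scored.** SAP 15.3.1, note 4: "If there are multiple visits within a visit window, the visit closest to the target date will be used". SAP 15.6.1 applies the same principle in the rule that starts "For categorical data, if there are two values within a time window", but breaks ties differently: towards the value before target, where 15.3.1 prefers the scheduled visit.
- **What enters a window.** "Exit/withdrawal and unscheduled visits will be slotted to the appropriate planned visit" (SAP 15.3.1). The protocol's Schedule of Activities marks both SLEDAI-2K assessments, the PGA and the Flare Index for unscheduled visits. It also allows ±28-day visit windows where COVID-19 interferes.
- **Windows** (target, first day, last day): "365 | 351 | 392 | 170 | Week 52"; "449 | 435 | 476 | 190 | Week 64"; "729 | 701 | 742 | 240 | Week 104".
- **Responder rule.** For disease control, SAP 7.1.1 requires "Not a TF at the current or any prior visit (TF includes consideration of corticosteroids and immunosuppressants"). SAP 15.6.4 lists the same three components: score, no failure, no withdrawal. SAP 15.6.15 counts failures that arise before the analysis visit.
- **Other steroid anchors.** SAP 15.6.15.1 averages over the day of assessment and the 6 days before it. SAP 7.2.1 and 15.6.5 add a separate 0 mg 7-day average at the assessment for clinical remission. SAP 15.6.15.4 ties the last steroid interval of Week 104 completers to the exit visit.

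**The concern.** The primary and both major secondary endpoints are meant to be response without rescue. That holds only if medication is checked up to the moment the disease score is taken. Here the two are dated by different rules. For disease control, steroid and immunosuppressant use enters only through failure status, so nothing else in the endpoint catches a failure dated after the cut-off but before the scored assessment. The error can run only one way for an individual, from non-responder to responder, and Week 52 is the first test in the step-down sequence.

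**Working it through.** **1. The plan's own figure.** Protocol 10.2 gives at least 98% power for 10% vs 35% with 70 and 140 participants, two-sided 5%. A normal-approximation calculation gives 98.9% and exact enumeration of the likelihood-ratio test gives 99.0%, so the figure reproduces. The point does not depend on it.

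**2. Order of dates.** Let E be the earliest efficacy date in the window and S the date of the scored SLEDAI-2K. S is one of the dates in the window, so E ≤ S always. Read literally, a failure arising after E and up to S is not counted at that visit. With one date in the window, E = S and nothing is lost.

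**3. Largest gap S − E**, from the windows in SAP 15.3.1:

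| Visit | Score on target | IBA score on both dates | Early record is PI, PGA or flare only |
|---|---|---|---|
| Week 52 | 365 − 351 = 14 | 378 − 351 = 27 (28 on a tie) | 392 − 351 = 41 |
| Week 64 | 449 − 435 = 14 | 462 − 435 = 27 (28 on a tie) | 476 − 435 = 41 |
| Week 104 | 729 − 701 = 28 | 742 − 701 = 41 | 742 − 701 = 41 |

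In the middle column the later score must be the closer one to target. Day 351 is 14 days early, so the later score can be at most 13 days late (Day 378). It can be 14 days late (Day 379) if a tie goes to a later scheduled visit. At Week 104, Day 701 is 28 days early and the last day, 742, is only 13 days late, so the whole window qualifies.

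**4. A hypothetical steroid case at Week 52.** A PI flare record falls on Day 352. Prednisone 20 mg/day starts on Day 353 after 0 mg, and the IBA scores ≤2 on Day 365. The 7-day average after two days is 2 × 20/7 = 5.7 mg/day, so the >5 mg/day rule is first met on Day 354, after the Day 352 cut-off. Under 15.6.15.3 this is not a failure at Week 52. Under 15.6.15.1, the average on Day 365 is 7 × 20/7 = 20 mg/day, which is a failure. The two passages give opposite answers.

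**5. Exposure by visit.**
- *Week 52:* any rescue, with the conflict in step 4 for steroids.
- *Week 64:* non-steroid rescue (immunosuppressants, restarted belimumab, prohibited drugs). Steroids in the 7 days up to the assessment fail the separate 0 mg test; those stopped more than 6 days before it do not.
- *Week 104:* non-steroid rescue. For steroids, 15.6.15.4 and 15.6.15.3 conflict.

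**6. Size per participant.** One participant is 1/70 = 1.4 points in Arm A or 1/140 = 0.7 points in Arm B. Unadjusted likelihood-ratio p-values near the threshold:
- 7/70 vs 30/140 gives p = 0.033; one extra Arm A responder (8/70) gives 0.067.
- 7/70 vs 28/140 gives p = 0.057; one extra Arm B responder (29/140) gives 0.044.

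At the design rates, power falls from 98.9% to 98.0%, 96.6% or 88.6% if Arm A alone gains 1, 2 or 5 points. It falls to 98.6%, 98.4% or 97.5% if both arms gain the same. These shifts are assumptions.

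**The case against.** - **All rescue at all three visits.** A reader might infer that any rescue is ignored at Weeks 52, 64 and 104 alike. The documents do not support that: Week 64 has its own steroid test, Week 104 steroids have a competing anchor, and failure carries forward, so one missed at Week 52 still counts later.
- **Direction of bias.** A reader might infer that late rescue is commoner in the control arm and dilutes the comparison. Nothing in the documents establishes this. Either arm can be misclassified, so the net bias cannot be signed.
- **SLEDAI-2K look-back.** The index covers the preceding 10 days (SAP 15.6.3). In the case above, a Day 365 score reaches back to Day 355, so features weighing more than 2 must have gone by Day 354. This makes the on-target case narrow at Weeks 52 and 64 (14 − 10 = 4 days). It matters less for a late IBA score (41 − 10 = 31 days).
- **Narrow trigger.** SAP 15.5.2 keeps unscheduled visits out of most summary tables, which sits badly with slotting them in 15.3.1. If it prevailed, PI and IBA assessments of one visit held on different dates would remain.
- **Adjudication.** All potential failures are adjudicated, and those through Week 52 are reviewed before unblinding. This stands as a safeguard, but 15.6.15.3 lets adjudicators amend the date of the failure, not the cut-off for the visit. No text tells them to look as far as the scored assessment.
- **Supportive endpoints.** SAP 7.10.1 (Week 52) and 7.3.6.2 (Week 104) check steroids and immunosuppressants back from the visit day, but neither is the main analysis. Neither addendum changes the rule.

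**Conclusion.** The rules are wrong as written, within limits. The failure cut-off can only equal or precede the scored SLEDAI-2K, so rescue between the two can be credited as response to the extent set out by visit above. This needs several efficacy dates in the window, a scored date later than the earliest, a failure arising in between, a qualifying score and no earlier failure. The documents do not say how many participants meet all of these. At the design rates a handful would leave power high; near the significance threshold, one could change the Week 52 conclusion in either direction. The p-values are unadjusted, whereas the planned analysis is a covariate-adjusted logistic regression.

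**What to change.** In SAP 15.6.15.3, set the failure cut-off for each endpoint visit to the date of the SLEDAI-2K actually scored: the IBA date for the primary and major secondary endpoints, and the PI date for PI endpoints. Count failures arising up to that assessment, and state how same-day starts are handled so that this agrees with the before-the-visit limit in 15.6.15. Use the imputed target date only when no scored assessment exists. Reconcile 15.3.1, 15.5.2, 15.6.1, 15.6.15.1, 15.6.15.3 and 15.6.15.4, including the two tie-breaking rules and the steroid anchors.

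The second addendum follows the first database lock and primary analyses, so the re-dated Week 52 result should be reported as a sensitivity analysis rather than replace the primary one.

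The cost is a short text change and a small programming change. A few participants may move from responder to non-responder, and one participant may have different IBA and PI cut-off dates at the same visit.

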15.6.15.4. Steroids

- SLE-related steroids are steroids where medication type is marked as ‘Systemic Lupus Erythematosus (SLE)’ (CMTYPCD=156), regardless of reason for medication (CMREAS).
- Total steroids include steroids for SLE and non-SLE reasons.
- Baseline dose is the 7-day average based on the 7 days **prior** to, but not including, treatment start date.
- The average steroid dose on any post baseline day is the sum of the steroids on that day and the prior 6 days divided by 7, so long as all days are post the baseline visit.
- The first day that the TF rule
 - Received a prednisone equivalent corticosteroid 7-day average dose of >5 mg/day after Week 26 visit

is applied will be when all values used in the average steroid dose are after Week 26 visit (not including the week 26 visit day) i.e. 7 days after Week 26 visit

- The final week interval for subjects who complete Week 104 will be 7 days prior to the exit visit date; [exit visit -7 days]. to [exit visit -1 day]. The day of Week 104 visit will not be included.
- The final interval for subjects who withdraw early will be the 7 days up to and including the exit visit date; [exit visit/early withdrawal date -6]. to [exit visit/ early withdrawal date]. The day of withdrawal will be included.
- The above rules may miss a subject who starts/increases a steroid close to the day of withdrawal. In this situation it is possible that the subject may have withdrawn prior to the end of the interval for computing their 7-day average exceeding the TF threshold. Hence all subjects whose dose of steroid increased within 7 days (including day of withdrawal) of withdrawal, and have not already crossed the dose threshold for TF based on the 7-day average rule, will be output for clinical adjudication. If clinical adjudication determines these to be treatment failures the date of treatment failure will be set to the date of withdrawal.
- A subject who is receiving 0mg of steroid at baseline will be allowed to take ≤5mg of steroid post baseline without being considered a treatment failure.
- Intra-articular steroids are not included in average steroid dose calculations.
- Subjects with more than one dosing regimen that involves alternate day dosing will be reviewed to ensure the daily dose is calculated correctly.
- The 7 day average steroid >5mg/day rule will include SLE and non-SLE steroids in the identification of potential treatment failures. Treatment failure review will

exclude cases where the 7 day average steroids is >5 mg/day due non-SLE steroids on a by subject review basis.

Intra-articular (IA) injections

- Participants may receive intraarticular injections during the study with the exception of within 8 weeks prior to the key efficacy endpoints (i.e. Week 52, 64, and 104). A participant who receives any intraarticular injection(s) within 8 weeks before to the Weeks 52, 64, and/or 104 visits will be defined as a treatment failure.

Corticosteroids for Reasons Other Than SLE Disease Activity

Corticosteroids for non-SLE reasons (e.g., asthma, contact dermatitis, etc) may be given short-term at higher doses than ≤ 5 mg/day according to the following guidelines:

- Up to 750 mg (prednisone) for 1 day,
and/or
- Up to 60 mg/day (prednisone) for 2-3 days ,
and/or
- Up to 40 mg/day (prednisone) for 4-7 days.

After Week 26, the duration of high dose corticosteroids use for reasons other than SLE must not exceed 7 days, after which time, tapering should begin. The total corticosteroid dose must be tapered to ≤ 5 mg/day within 21 days of the 1st dose of a course of high dose corticosteroids given for non-SLE reasons. In addition, no new high dose corticosteroids for reasons other than SLE are allowed that result in an average corticosteroid dose of >5 mg/day during the intervals starting 8 weeks before the key efficacy visits at Weeks 52, 64, and 104. During the intervals of 8 weeks before these efficacy endpoints, any new high dose corticosteroid use will declare the participant as a treatment failure. The day of the Week 44, 56, and 96 visits will count as the start of these 3 intervals (imputed visit date will be used for Week 56).

NOTE: Inhaled and topical corticosteroids are allowed throughout the course of the study

15.6.15.5. Anti-malarials

Dose of anti-malarial at baseline is the dose the subject received on the treatment start date (Day 1). If a patient is receiving an anti-malarial at baseline it will be assumed that the dose is stable and not a loading dose.

Anti-malarial therapies may be continued, or dose adjusted during the study.

For non-SLE reasons (e.g., for the experimental treatment of COVID-19) an anti-malarial may be initiated for a subject not previously on an anti-malarial, or dose increased above

the common allowable maximum doses (defined below) according to the following guidelines, for short-term treatment:

- < 21 days treatment duration
- Not during the intervals within 8 weeks before the key efficacy visits (actual visit date) at Weeks 52, 64, and 104.

An anti-malarial may be replaced by another anti-malarial due to documented toxicity or lack of availability at any time during the study.

Clinical loading dose is permitted for initiation or replacement. Whether or not the dose was a loading dose will be assessed by clinical adjudication.

The common allowable maximum doses of anti-malarial drugs are:

- Hydroxychloroquine – 400 mg/day
- Chloroquine – 500 mg/day
- Quinacrine – 100 mg/day

For compounded anti-malarials, no individual component may exceed the maximum dose above.

NOTE: The use of anti-malarials for anti-malarial prophylaxis is permitted.

